5.6 Data Analysis

Analysis Plan and Power Calculations: The primary and secondary hypotheses will be calculated using within group t-tests using the Statistical Package for the Social Sciences (SPSS). A statistical power analysis was performed for sample size estimation. The effect size was estimated to be medium (0.50) using Cohen's (1988) criteria. With an alpha = .05 and power = 0.80, the projected sample size needed with this effect size is approximately N = 34 to conduct a single sample t-test. Thus, our proposed sample size of N = 50 should be more than adequate to analyze the main hypothesis for this study and should also allow for expected attrition and the analysis of our secondary hypotheses.

Interpretation: Interpretation of these hypotheses should demonstrate whether the Genecept® Assay and the G-DIG tool are beneficial to Veteran prescribed polypharmacy in order to reduce polypharmacy and improve clinical symptoms. The primary limitation to this study is that there is no control group, so attribution of any change to the pharmacogenetic assay should be done with reservations. If this study shows promising results, future studies should include a randomized control group. Another limitation is sample size. Though with our estimated effect size, we should have power to detect significance, larger sample sizes are preferred to increase generalizability to a larger population.

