Study staff will contact the participant at 6 and 12 weeks by phone to conduct phone interviews to repeat the measures of depression, anxiety, PTSD, insomnia, pain, drug and alcohol use, quality of life, side effects, and adherence. Study staff will also complete a CGI-I assessment. Study staff collecting the participant ratings will be blind to any medication changes made until the end of the subject's participation in the study. After the 12 week assessment, study staff will review the medical record to determine changes in medications.

During the consenting process, subjects will be presented with an additional consent in order to allow researchers to add the data into a research repository. Subjects can choose whether or not to participate. If they do, their data will be entered into the repository. If they do not, their data will be kept during the time of the study and maintained as per IRB rules and regulations.

Risk/Benefit Ratio: This study naturalistic study presents only a limited risk to subjects and is associated with the possible benefits of reducing polypharmacy, improving symptoms, and reducing the risk of adverse events. Essentially, the only intervention in this study is the provision of additional data to the provider that may aid in choosing more appropriate medications.

Potential risks of this study include participants becoming uncomfortable with questions asked on the survey, potential for breach of confidentiality, and the risk that if the assay provides poor advice, a medication chosen may not have the desired effect (of course this is always a risk when prescribing any medication and is not exclusive to this study). Since this is a naturalistic study,

side effects of medication treatment are an expected part of treatment as usual and will be handled by their provider as part of their regular clinical care.

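### The within-group t-tests in section 5.6 leave the week-6 scores of week-12 dropouts unused for H3 and H5, and no sensitivity analysis allows for patients who share a provider

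*Combined protocol and SAP*

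**What the plan says.** Section 5.6 covers all primary and secondary hypotheses in one sentence: "The primary and secondary hypotheses will be calculated using within group t-tests using the Statistical Package for the Social Sciences (SPSS". It names no time point, missing-data method, repeated-measures model or provider term. On size it says "projected sample size needed with this effect size is approximately N = 34 to conduct a single sample t-test", and that enrolling 50 "should also allow for expected attrition and the analysis of our secondary hypotheses".

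The follow-up data are richer than a two-point test needs. Section 5.1 states: "Study staff will contact the participant at 6 and 12 weeks by phone to conduct phone interviews to repeat the measures", and "Study staff will also complete a CGI-I assessment". These raters are partly protected from bias: "Study staff collecting the participant ratings will be blind to any medication changes made" until the patient's participation ends. The provider's own CGI-I is collected only where an appointment falls within the visit window. Section 5.7 keeps data already collected from patients who withdraw.

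Medication counts come from chart review at baseline and 12 weeks (section 5.5), and section 5.1 adds: "After the 12 week assessment, study staff will review the medical record to determine changes in medications". Under sections 5.1 and 5.2, providers are sub-investigators who refer their own patients and make the final medication decisions. They may have more than two patients each. Section 5.6 frames the conclusion as whether the assay and tool are "beneficial to Veteran prescribed polypharmacy in order to reduce polypharmacy and improve clinical symptoms".

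**The concern.** A paired t-test uses only patients with both scores. At week 12, a patient who gave a baseline and a week-6 score and then left contributes nothing. If leaving is related to how the patient was doing at week 6, those who remain are a selected group and their mean change is biased. The plan meets attrition only with extra patients, and extra patients do not remove that bias. In a single-arm, open-label study no control group shares the same selection. H3 and H5 are labelled secondary, although section 5.5 calls the CGI the primary measure of clinical effectiveness.

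The second issue is independence. The outcomes for polypharmacy (H1), plan changes (H2) and medication costs (H4) partly measure what providers do, so patients of one provider may change alike. If they do, the t-test understates uncertainty for any conclusion that reaches beyond the participating providers.

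**Working it through.** **1. The plan's own figure.** Inputs from section 5.6: effect size 0.50, alpha 0.05, power 0.80. Sidedness is not stated; two-sided reproduces the figure. Power of a one-sample t-test comes from the noncentral t distribution with n-1 df and noncentrality 0.5 x sqrt(n):

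| n analysed | 33 | 34 | 40 | 50 |
|---|---|---|---|---|
| Power | 0.795 | 0.808 | 0.869 | 0.934 |

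N = 34 is correct. With independent patients and loss unrelated to outcome, 50 absorbs 1 - 34/50 = 32% loss. The margin is 50/34 = 1.47.

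**2. Selective dropout (H3, H5).** The documents give no dropout rate, correlation or mechanism, so all three are assumed. Week-6 and week-12 changes are standard normal with correlation r and no true change. Dropout after week 6 is logistic in the week-6 change, with slope 0.6 or 1.2 per SD. Then

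bias of completers' mean = r x (mean week-6 change among those who stay).

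Example: with slope 1.2 and 20% dropout, those who stay have a mean week-6 change of about 0.197 SD. At r = 0.55 the bias is 0.55 x 0.197 = 0.108 SD. Over r = 0.4-0.7 and both slopes, for 50 patients (20,000 simulated trials per setting):

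| Dropout | Size of bias (SD of change) | Two-sided rejection, no true change |
|---|---|---|
| 10% | 0.02-0.07 | about 5-8% |
| 20% | 0.05-0.14 | about 6-15% |
| 30% | 0.07-0.20 | about 7-23% |

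The sign depends on who leaves. If poor responders leave, the bias is towards improvement. If improved patients leave, it has the same size in the opposite direction: with slope 1.2, 20% dropout and r = 0.55 it is 0.11 SD against improvement, and false improvement is found in about 0.4% of trials. If dropout is unrelated to outcome there is no bias.

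**3. What week 6 adds.** The likelihood estimate using week 6 has bias of about 0.002 SD or less in the same settings. Its limits:
- If half of the dropouts leave before week 6 (slope 1.2), 0.02-0.08 SD remains. If all do, nothing is gained.
- If dropout depends on the unseen week-12 value (slope 1.2), completer bias is 0.11, 0.20 and 0.29 SD at 10, 20 and 30% dropout. The likelihood estimate still has 0.06-0.09, 0.11-0.17 and 0.16-0.25 SD.
- The precision gain is modest: a variance ratio of 1.02-1.14, assuming correlations of 0.5-0.8, 5-10% lost before week 6 and 10-20% after.

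**4. Shared providers.** The available text gives neither provider number nor ICC, so both are assumed. Design effect = 1 + (m-1) x ICC for m patients per provider. With no attrition, the 1.47 margin is used up at ICC = (50/34 - 1)/(m-1). Type I error is simulated for conclusions beyond these providers. Power of a test on provider means uses k-1 df (k providers) and noncentrality 0.5 x sqrt(k) / sqrt(ICC + (1-ICC)/m).

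| Providers x patients | ICC using up margin | t-test type I error, ICC 0.05 / 0.10 / 0.20 | Provider-means power at N = 50, same ICCs |
|---|---|---|---|
| 25 x 2 | 0.471 | 5.7 / 6.0 / 7.4% | 0.911 / 0.899 / 0.872 |
| 10 x 5 | 0.118 | 7.2 / 9.7 / 14.5% | 0.819 / 0.758 / 0.651 |
| 5 x 10 | 0.052 | 10.4 / 15.4 / 24.5% | 0.602 / 0.496 / 0.367 |

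With these providers taken as fixed, the t-test's error rate is 2.9-4.6%, slightly conservative. With 5 providers and ICC 0.10, unlimited patients would raise provider-level power only to 0.753.

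**The case against.** Section 5.6 does not prescribe a complete-case week-12 test; it names no time point at all. That is so. The consequence follows from how the named test works under its most natural reading, not from a stated rule.

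Missingness may also be small. Staff collect scores by phone and patients are paid per visit, and the staff CGI-I limits the loss from the provider's irregular rating. At 10% dropout the error rate barely moves, and the upper figures (0.20 SD, 23%) need 30% dropout, r = 0.7 and the steeper slope together. This stands, and it is why the size is given as a range.

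A reader might infer that dropout will exaggerate benefit. The documents do not say who is likely to leave, and the bias could equally run the other way. A reader might also infer that the medication count suffers the same loss. It is largely outside this point: it comes from chart review, and section 5.5 does not make that review depend on a completed week-12 call. H2 compares plans written around baseline. For H1, attrition and clustering therefore hardly compete for the same margin.

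On providers, the strongest objection is that adjustment is not cheap. Even with 10 providers and ICC 0.10, power is 0.758 before any loss, below the planned 0.80. This also stands. Section 5.6 already asks for caution over attribution, sample size and generalisability. That moderates the conclusion, but it mentions neither missing scores nor shared providers.

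**Conclusion.** The point holds in two parts of unequal weight.

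For H3 and H5, a better method is available from data already planned. Under the assumptions shown, the completer analysis is biased by about 0.02-0.20 SD in one direction or the other. The mixed model removes this when dropouts have a week-6 score, but not for earlier dropout or dropout that depends on unseen values.

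The provider part is real but conditional. It runs from trivial (many providers with about two patients each) to serious (few providers), and it applies only to conclusions beyond these providers. A reader might infer that the trial's error rate is 10-25%. That requires about five providers with an ICC of 0.05-0.20, and nothing in the available text establishes either. Sections 1.0 and 4.0 are not in the text reviewed, so the absence of a provider number is not held against the plan. Nor do the documents support calling 50 patients too few, because 34 is correctly calculated, or making a provider-level analysis primary.

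**What to change.** **Scales with a baseline (H5):** replace the paired t-test by a repeated-measures mixed model on baseline, week 6 and week 12 with unstructured covariance, and report week 12 minus baseline. Add a sensitivity analysis that shifts the missing week-12 values over a stated range.

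**CGI-I (H3):** it has no baseline value, so model weeks 6 and 12 against a rating of no change, with the blinded staff rating and the provider rating analysed separately. Before planning any analysis of CGI-S change, reconcile Appendix A (both CGI items at follow-up) with section 5.1 (CGI-I only).

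**Providers:** keep the t-test as primary for H1, H2 and H4. Record the referring provider as a data item. For all hypotheses, including H3 and H5, add a sensitivity analysis that allows for provider, by a random effect with small-sample df or a test of provider means. State that the t-test's error rate applies to these providers' patients unless change is uncorrelated within provider.

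**Clarification:** say that the week-12 chart review does not depend on a completed week-12 call, for patients who have not withdrawn permission.

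**Cost:** slightly more analysis work, which SPSS MIXED can handle, one recorded item and perhaps a few extra chart reviews. No extra patients or visits are needed. The precision gain is modest. With few providers the sensitivity analysis will be imprecise: at 5 x 10 the provider variance was estimated as zero in 24-37% of runs for ICC 0.10-0.05. That is a further reason not to make it primary.

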This is a 12-week open-label, naturalistic study of the provision of pharmacogenetic testing information to both providers and patients. Veterans who have been prescribed polypharmacy and are experiencing a sub-optimal effect will be eligible for the study. Medication providers who are participating in the study as sub-investigators will refer their own patients for the study. Participating subjects will sign informed consent and a sample will be obtained in order to complete the pharmacogenomic testing. Providers will utilize the pharmacogenetic assay results along with the G-DIG tool to design an optimized medication regime. The overall global level of symptoms and other patient symptoms measures will be administered at baseline, 6-weeks, and 12-weeks.

3. Methodology

Fifty Veterans within the VAPSHCS who are prescribed polypharmacy, as defined as five or more medications, with at least two prescribed for a mental health diagnosis, and have a sub-optimal treatment effect will be enrolled in this study. The provider's medication plans will be compared before and after the pharmacogenetic assay information is provided. Number of medications will be reviewed to determine any

reduction in polypharmacy and healthcare costs. The clinical global improvement scale (CGI) and patient assessments, including measures of depression, anxiety, PTSD, insomnia, pain, drug and alcohol use, quality of life, side effects, and medication adherence will be administered at baseline, 6-weeks, and 12-weeks.

List of Abbreviations

AE	Adverse Event
CRF	Case Report Form
DSMB	Data Safety Monitoring Board
G-DIG	Genomind Drug Interaction Guide
HIPAA	Health Insurance Portability & Accountability Act
IRB	Institutional Review Board
PHI	Protected Health Information
PI	Principal Investigator
PTSD	Post-Traumatic Stress Disorder
R&D	Research & Development
SAE	Serious Adverse Event
Sub-I	Sub Investigator
TBD	To Be Determined
VAPSHCS	VA Puget Sound Health Care System

Contents

Protocol Title:	6
1.0 Study Personnel	6
2.0 Introduction.....	6
3.0 Objectives.....	8
4.0 Resources and Personnel	9
5.0 Study Procedures.....	9
5.1 Study Design.....	9
5.2 Recruitment Methods.....	13
5.3 Informed Consent Procedures	14
5.4 Inclusion/Exclusion Criteria	14
5.5 Study Evaluations	15
5.6 Data Analysis	15
5.7 Withdrawal of Subjects.....	16
6.0 Reporting.....	16
7.0 Privacy and Confidentiality	17
8.0 Communication Plan	17
9.0 Information Security and Data Storage/Movement.....	17
10.0 References.....	18

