3.0 Objectives

The use of polypharmacy in Veterans, especially for the treatment of PTSD and traumatic brain injury, has increased over the past two decades, exposing Veterans to risks for drug-drug interactions and adverse side effects. Use of a pharmacogenetic tool that could give providers essential information needed to optimize Veteran's medication regimen has the potential to improve Veteran health outcomes, reduce risks for adverse events, and reduce treatment utilization costs.

This project is designed to evaluate the effectiveness of pharmacogenetic testing in individuals who are prescribed psychiatric polypharmacy. The study will test the following hypotheses:

- Use of pharmacogenetic testing and the G-DIG will reduce psychiatric polypharmacy.
- Use of pharmacogenetic testing and the G-DIG information provided to providers will result in changes to the medication treatment plan based on the new information.
- Use of pharmacogenetic testing and the G-DIG will improve overall clinical symptoms as measured by the CGI (secondary analyses).
- Pharmacogenetic testing and the G-DIG will reduce healthcare costs associated with medications (secondary analyses).
- Pharmacogenetic testing will reduce clinical symptoms of anxiety and depression and improve quality of life (secondary analyses).

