5.0 Study Procedures

5.1 Study Design

This is a 12-week open-label, naturalistic study of the provision of pharmacogenetic testing information to both providers and patients. Veterans who have been prescribed polypharmacy and are experiencing a sub-optimal effect will be eligible for the study. Medication providers who are participating in the study as sub-investigators will refer their own patients for the study. Eligible patients will be given the opportunity to participate in this study. Informed consent will be obtained by research staff who are not the potential participant's provider to avoid any undue pressure to participate.

If the potential participant signs consent, a cheek swab sample will be obtained in order to complete the pharmacogenomic testing. The genetic information will be sent to Genomind for processing using only a unique study number. No personal health information will be shared with the sponsor. Participants will be asked to complete a short battery of psychological measures, including measures of depression, anxiety, PTSD, insomnia, pain, drug and alcohol use, quality of life, side effects, and medication adherence (See Appendix A).

After the participant signs the consent form, they will enter a 2-week baseline period. During these 2 weeks, the pharmacogenetic test results will be available online for providers. Prior to receiving the results, providers will draft an initial medication optimization plan without the benefit of the pharmacogenetic information. The provider will also complete a Clinical Global Impression-Severity (CGI-S) rating of overall severity of symptoms for their client, and will document the participant's primary and secondary (if any) diagnoses.

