When the results of the pharmacogenetic testing are ready, providers will review results using a secure web-based program and will utilize the G-DIG tool in order to determine the optimal medication regime for the patient, based on their individual genetic profile. Genomind will provide training to all investigators prior to the study start regarding the interpretation of the pharmacological assay and the use of the G-DIG tool. Genomind representatives will be available throughout the duration of the study for consultation regarding the interpretation and implementation of the testing results. For each provider, consultation is mandatory for the first two subjects and then available as needed for further subjects. If the patient is on a medication that is not currently listed in the G-DIG, the provider will inform the sponsor, and that medication will be added to the G-DIG tool. All final decisions about changing dosage, adding medications, or removing medications will be determined by the provider.

The provider will design an optimized, individualized medication regimen for the participant and document this revised plan. All clinical decisions regarding medical treatment and making any changes to medications will be made by the treating provider and their patient. Any medications that might be recommended by the testing results but are not provided by the VA's pharmacy (not on formulary) will be noted. Providers will then contact their patients by phone, mail, and/or schedule an in-clinic appointment for the subject (this can be scheduled at the initial consent appointment) to review the pharmacogenetic assay results and implement the medication optimization plan. Any medication changes will be dispensed by the pharmacy either in person or can be sent to the participant by mail. The provider will have 2 weeks (± 2 weeks) to review these results and contact the patient.

After the 2-week baseline, future appointments between the provider and the participants will be conducted consistent with treatment as usual. It is recommended that appointments around 6 and 12 weeks (within a three week buffer) be scheduled, but this is up to the discretion of the provider and the needs of the patient. The provider will complete a CGI-Improvement (CGI-I) measure at appointments within the 6 and 12 week windows, as available.

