5.4 Inclusion/Exclusion Criteria

Inclusion Criteria

1. Currently receiving outpatient treatment for a mental health diagnosis within the VA Puget Sound Health Care System from a provider who is a sub-investigator on this study.
2. Currently experiencing a sub-optimal medication response as assessed by either continued symptoms or medication side effects, which in the opinion of their treating provider would indicate a change in medications would be warranted.
3. Currently prescribed polypharmacy, as defined as five or more medications, with at least two being for a mental health diagnosis. Also allowable would be one medication for a mental health diagnosis and another medication for side effects related to a medication prescribed for the mental health diagnosis.
4. Between the ages of 18 and 75.

Exclusion Criteria

1. Any mental or physical health diagnosis, which in the opinion of their treating prescriber would prevent them from being compliant on a medication regimen or being able to complete the study measures.
2. Current/active diagnosis of severe alcohol or drug use disorder.
3. Serious medical or mental health symptoms requiring immediate stabilization and/or hospitalization.
4. Impaired decision making capacity that in the clinical judgement of their provider would affect their ability to provide informed consent.
5. Self-identification as being currently pregnant.

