5.5 Study Evaluations

Measures:

The primary measure to determine clinical effectiveness is the Clinical Global Improvement Scale. This scale will be completed both by the provider and the study coordinator (or study personnel collecting the assessment measures).

The number of medications and treatment utilization will be collected by chart review of the subject's medical record at baseline and at 12 weeks to determine any change in the number and type of medications prescribed.

Any differences between the initial medication plan developed by the provider prior to receiving the pharmacogenetic assay results, the medication optimization plan developed by the provider after the use of the G-DIG tool, and actual clinical practice will be noted. The number and cost of medication changes will also be evaluated.

Participant assessments administered at baseline, 6 and 12 weeks will include measures from the Behavioral Health Lab (BHL; Oslin et al., 2006). These measures will include a demographic questionnaire, GAD-7 (Anxiety), PHQ-9 (Depression), PCL-5 (PTSD), Insomnia Severity Index, Chronic Pain, Screening for Alcohol and Drug use, RAND Health Survey, and Side Effects and Adherence (See Appendix A). The results of the BHL assessments will be placed into the subject's medical record. Participants will also be asked about smoking.

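### Medication changes already planned before the assay count toward the polypharmacy result, and the pre-assay plan that could separate them is not used as its reference

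*Combined protocol and SAP*

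**What the plan says.** The first hypothesis in section 3.0 is that testing plus the G-DIG reduces psychiatric polypharmacy. The second is that the information "will result in changes to the medication treatment plan based on the new information". Only the remaining three are marked as secondary.

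- **Measure.** The Abstract (3. Methodology) ties any reduction in polypharmacy to the number of medications. Section 5.5 takes that number from the chart "at baseline and at 12 weeks to determine any change in the number and type of medications prescribed".
- **Test.** Section 5.6: "The primary and secondary hypotheses will be calculated using within group t-tests". The sample size assumes a standardized effect of 0.50, alpha .05 and power 0.80. This gives about 34 patients, and 50 are planned.
- **Who enters.** Inclusion criterion 2 (section 5.4) requires a sub-optimal response "which in the opinion of their treating provider would indicate a change in medications would be warranted".
- **Two plans.** In section 5.1, before results arrive, "providers will draft an initial medication optimization plan without the benefit of the pharmacogenetic information". Afterwards: "The provider will design an optimized, individualized medication regimen for the participant and document this revised plan".
- **Use of the plans.** The Abstract says that the provider's "medication plans will be compared before and after the pharmacogenetic assay information is provided". Section 5.5 says that differences between the initial plan, "the medication optimization plan developed by the provider after the use of the G-DIG tool, and actual clinical practice will be noted". It then adds that the number and cost of medication changes will be assessed, without saying what they are changes from.
- **Caveat.** Section 5.6 names the missing control group as the main limitation and asks for caution in attributing change to the assay. The same paragraph expects the results to show whether the assay and the G-DIG are of benefit.

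**The concern.** A patient enrolled because a change is due would probably have had some change without the assay. The initial plan records what the provider intended at that point. If it listed stops and they were made by week 12, the chart count falls and the within-group test credits that fall to the intervention. If it listed starts, the count rises and a real contribution from the assay is partly hidden.

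What is at stake is the meaning of the main result. A significant fall could reflect the assay, the pre-assay intentions, or both, and the planned test cannot tell them apart. The general caveat tells readers to be cautious but gives them no figure. The study already documents material that could supply one.

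**Working it through.** **1. The plan's own figure.** For a two-sided one-sample t-test, power = P(T > t*) + P(T < −t*), where T is noncentral t with n − 1 degrees of freedom and noncentrality d√n, and t* is the 97.5% point of central t. Sidedness is not stated in section 5.6; the two-sided version matches.

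- d = 0.50, n = 33: power 0.795.
- d = 0.50, n = 34: noncentrality 0.50 × √34 = 2.92, power 0.808. This reproduces the stated 34.
- d = 0.50, n = 50: noncentrality 0.50 × √50 = 3.54, power 0.934.

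The sample size is right for the test described. The open question is what the 0.50 measures.

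**2. What the count change contains.** For each patient let B be the baseline count, P0 the count under the initial plan, P1 the count under the G-DIG plan and W the 12-week count. Then

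W − B = (P0 − B) + (P1 − P0) + (W − P1).

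This is an exact arithmetic identity, not a causal split.

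- P0 − B was decided without the results.
- P1 − P0 is the revision after the results. It combines the assay, the G-DIG and vendor consultation, which section 5.1 makes mandatory for each provider's first two subjects.
- W − P1 holds intentions not carried out, later clinical events and later assay-guided changes. The last can include changes by other clinicians, because section 5.1 (Pharmacogenetic Sample) lets results be released to them.

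The planned test uses only the total.

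**3. Illustration: no assay contribution.** The documents give no rate of pre-planned change and no SD for the count, so the following values are assumptions. Suppose the assay adds nothing and the initial plans lower the count by d0 SD. The chance of a significant reduction at N = 50 is P(T > t*) with noncentrality d0√50:

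| d0 | d0√50 | Chance of a significant reduction |
|---|---|---|
| 0 | 0 | 2.5% |
| 0.1 | 0.71 | 10% |
| 0.2 | 1.41 | 28% |
| 0.3 | 2.12 | 55% |
| 0.4 | 2.83 | 79% |
| 0.5 | 3.54 | 93% |

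**4. Illustration: the opposite direction.** If later changes lower the count by 0.50 SD but the initial plans raise it by 0.20 SD, the net change is 0.50 − 0.20 = 0.30 SD. From the table, the chance of a significant reduction falls from 93% to 55%. Switches leave the count unchanged.

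**5. Precision of a contrast against the initial plan.** Assume that the contrast has the same SD as the total change. The 95% CI half-width is t*/√n: 0.28 SD at n = 50, and 0.32 SD at n = 40 (20% attrition assumed; no rate is given). Again as illustration, if a share f of a 0.50 SD change was pre-planned, the remainder is 0.50 × (1 − f):

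| f | Remainder (SD) | Power at N = 50 | N for 80% power |
|---|---|---|---|
| 25% | 0.375 | 0.74 | 58 |
| 50% | 0.25 | 0.41 | 128 |
| 75% | 0.125 | 0.14 | about 505 |

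If P1 − P0 varies less than the total change, power is higher than shown.

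**The case against.** The strongest reply is that much of this is already planned. Section 5.5 sets up a three-way comparison of initial plan, revised plan and practice, and it assesses the number of medication changes. The second hypothesis is not marked as secondary and falls under the t-test sentence, which implies some numeric before-and-after measure. Section 5.6 also discloses the missing control group and recommends a randomized one in future.

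Most of that stands. A reader might infer that the pre-assay plan is ignored or that nothing about it is counted; the documents do not support that. The remaining gap is narrower. No medication count under the initial plan is defined, the reference for the number of changes is not given, and nothing sets the initial plan beside the polypharmacy result. A general caveat does not fill that gap.

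A reader might also infer that criterion 2 means a reduction had been decided, so that the test is biased toward success. The criterion requires only that a change be warranted, on account of symptoms or side effects. Adding or switching drugs would meet it equally well.

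Finally, the link between the chart count and the first hypothesis is inferred. The protocol assigns no endpoint by name, and it does not say whether all drugs or only psychiatric drugs are counted. The inference is strong because no other measure of polypharmacy is described.

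**Conclusion.** The point holds in this limited form. As planned, the test of reduced polypharmacy credits the intervention with any change that was already in the pre-assay plan and carried out by week 12. The documented plan that could separate such changes is not used as the reference.

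The size cannot be derived from the documents, and the direction is open. The 28%, 55% and 93% figures show only that a positive result with no assay contribution is possible. They rest on assumed pre-planned reductions of 0.2, 0.3 and 0.5 SD and are not estimates for this trial. The stated sample size is not in error.

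It would go too far to read P1 − P0 as the causal effect of the assay. It bundles the assay with the tool and the consultation, and the initial plan comes from a provider who knows that results are coming. The contrasts inform attribution but do not replace a control group. The change is worth making because it affects what the trial can conclude and costs little.

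**What to change.** Keep the planned test on the baseline-to-12-week count. Add the following:

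1. Record both plans drug by drug (stop, start, continue, switch), on the same drug list as the chart count, with the initial plan dated before results are opened.
2. Report beside the main result, each with a 95% CI: (a) G-DIG-plan count minus initial-plan count, and (b) 12-week count minus initial-plan count. Contrast (a) can also serve as the numeric measure for the second hypothesis's planned within-group t-test.
3. State with them that (a) reflects assay, G-DIG and vendor consultation together; that (b) also includes unimplemented intentions, later clinical events and later assay-guided changes, including those by other clinicians given the results; that the provider knew results were coming when writing the initial plan; and that neither contrast substitutes for a control group.
4. In section 5.6, base the attribution statement on these contrasts, not on the raw change alone.

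The cost is a structured form for two plans already being documented, a little provider time and two added estimates. No new visits or patients are needed. The form has to be in place from the start, because free-text plans may not yield counts later. The assay-related estimate may turn out smaller and less precise than the raw change, and the report should say that power for it may be well below 80%.
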